8.8 Multi-center Studies

Approximately 100 patients will be enrolled from 10 medical centers in Taiwan. With the intention of pooling the data for analysis, all the investigators from participating institutions will follow the study protocol and conduct the clinical trial to improve the consistency across centers. All the data defined on CRF will be collected and managed via a centralized process. A data validation plan will be developed to define the validation rules to check the data. All data from the 10 sites will be examined based on the data validation plan. If any discrepancy or illogic data is found, data query will be sent for clarification. All collected clinical data will be summarized with respect to demographic characteristics, efficacy and safety observations.

8.9 Data Management System and Analysis Software

The data collected will be entered into the study database against the paper CRF. Database backup is exhibited by data management personnel. The data will be exported to the Statistical Analysis System® (SAS) for Windows (Version 9.4 or higher, SAS Institute, Cary, North Carolina, USA) to generate the subject listings, tabulations, and statistical analyses.

8.10 Coding Dictionary

The system of variable coding will follow rules of SOPs. During the study, Data manager will follow the SOP to enter and manage the CRFs. In order to create a

standard language that is comparable across all therapeutic teams and provide standardization for statistical analysis, adverse events recorded on the paper CRF will be coded by medical dictionaries/thesaurus. In this study, the Medical Dictionary for Regulatory Activities (MedDRA) version 21.0 or higher will be used to map adverse events verbatim to Preferred Terms (PT) and System Organ Class (SOC)

8.11 Data Handling and Transfer

All collected clinical data will be collected via paper CRF by study coordinator, and will be managed centralized and stored in the clinical data management systems. No external data will be imported to the system. The system of variable coding will follow rules of SOPs. During the study, Data manager will follow the SOP to enter and manage the CRFs. After data clean and data lock process, all the clinical data will be exported as SAS datasets and stored in a read-only space. Statistician will perform the statistical analysis based on the SAS datasets.

8.12 Programming Specifications

The summary statistics for continuous variables will be entitled as Number, Mean \pm SD, Median, Range and 95% C.I. in the table, which represent the number of observations, mean value plus/minus standard deviation, median value of observations, minimum and maximum, lower bound and upper bound of the 95% confidence interval Range (minimum and maximum) and 95% confidence interval (lower and upper bound) are given in parentheses.

Unless otherwise noted, the summary statistics for continuous variables will be printed out to one decimal place except for the standard deviation and confidence interval. The standard deviation and confidence interval will be expressed to 2 decimal places. If the summary statistics cannot be obtained, it will be printed as "--"

For categorical variables, number and percentage will be presented as summary statistics. All table percentages will be reported with one decimal point unless otherwise specified.

The p-value will be reported to 3 decimal places. An asterisk indicates the statistical significance. P-value less than 0.001 will be reported as "<0.001*" and p-value greater than 0.999 will be expressed as ">0.999". If the p-value cannot be computed, p-value will be printed as '--'.

9 SUMMARY OF STUDY DATA

All the statistical analysis will be performed and categorized by the subgroup of with anti-fibrotic drug and no anti-fibrotic drug. The summary tables will be tabulated with columns of the two subgroups. The relevant population size will be annotated in the tables.

Continuous variables will be summarized by descriptive statistics: number of observations, mean, median, standard deviation, range, and 95% confidence interval. Frequency counts and percentages of observed levels will be reported for categorical variables. The denominator of percentages will be the number of subjects with valid assessment results. Subjects with missing data will not be included in the number of denominator.

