8.4 Covariates and Subgroups

Subgroup analysis will be conducted based on the prescription of nintedanib and pirfenidone. All enrolled subjects will be grouped as “no anti-fibrotic drugs” and “with anti-fibrotic drugs”. Subject had no record of anti-fibrotic drugs during the observation will be categorized as “no anti-fibrotic drug”. In contrast, the subjects with at least one record of anti-fibrotic drugs will be categorized as “with anti-fibrotic drugs”.

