8.7 Adjustments for Multiplicity

The study was not aimed to show significant difference between treatment groups and no hypothesis testing will be performed. Hence there is no need to adjust for multiplicity.

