11.3 Primary Endpoint Analysis

Annual declines will be summarized with descriptive statistics including Number, Mean \pm SD, Median, Range and 95% C.I. Annual decline will be tested by paired t-test to show if significant change. The Wilcoxon sign rank test will be used if the normally distributed assumption is violated. The test is two sided and the significant level is set as 0.05. The sas procedure used for the tests is listed as follow.

Statistical Test	SAS procedures and option
Shapiro-Wilk test	PROC UNIVARIATE NORMALTEST
T-test	PROC UNIVARIATE MU0=0 ALPHA=0.05
Wilcoxon sign rank test	PROC UNIVARIATE MU0=0 ALPHA=0.025

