11.6 Interpretation and Conclusion

The change from baseline endpoints will be assessed by two-sided paired T-test or Wilcoxon signed rank test under significance level 0.05. Once the p-value is lower than the significance level, the significant change could be claimed.

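### Read literally, the SAP tests change from baseline separately in the treated and untreated columns, so identical declines can get discordant significance verdicts

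*SAP*

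**What the plan says.** SAP 8.4 splits patients by use during observation: "the subjects with at least one record of anti-fibrotic drugs will be categorized as" treated, and everyone else is untreated. SAP 9 then says that "All the statistical analysis will be performed and categorized by the subgroup of with anti-fibrotic drug and no anti-fibrotic drug" and that "The summary tables will be tabulated with columns of the two subgroups". It mentions neither an all-patient column nor a difference column.

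The tests are in SAP 11. Section 11.1 sets a null of zero annual decline. Section 11.3 adds: "Annual decline will be tested by paired t-test to show if significant change", with the Wilcoxon signed-rank test as fallback, and "The test is two sided and the significant level is set as 0.05". Section 11.4 applies the same procedure to SGRQ, CAT and 6MWT. On display, SAP 8.12 says "An asterisk indicates the statistical significance". On interpretation, SAP 11.6 says "Once the p-value is lower than the significance level, the significant change could be claimed".

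Other sections point elsewhere:
- SAP 8.7 says "The study was not aimed to show significant difference between treatment groups", and the same sentence goes on to rule out hypothesis testing altogether.
- SAP 8.3 makes all eligible patients the main analysis population.
- Protocol 9.7.1 plans the tests of change with no drug split.
- Protocol 9.9 would drop stratified analyses if the small sample were judged harmful.
- SAP 12 declares no differences from the protocol.

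**The concern.** Two one-group tests against zero do not compare the groups. Whether each p-value falls below 0.05 depends on the size of the decline, its variability and the number of patients in that column. At the same true decline the larger column reaches significance more often, and even equal columns can differ by chance.

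If both columns carry their own p-value, asterisk and permitted claim, a table can show a significant decline in one and none in the other when the patients are declining at the same rate. Without a between-group estimate beside it, the reader has nothing that measures the contrast. The sponsor markets one of the two drugs that define the treated column, so an accidental impression of benefit or harm matters. Splitting the cohort also costs power for the question the protocol does ask, whether lung function changes from baseline in this population.

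**Working it through.** **What the plan supplies.** N is about 100, set by recruitment feasibility (Protocol 9.5, SAP 7.4). The test is two-sided at 0.05 (SAP 11.3). The plan gives no power figure to reproduce, and no decline, SD or treated/untreated split. As a check on the test alone, the one-sample t-test rejects 5.0% of the time when the true decline is zero.

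**What is assumed.** The same true decline of 5 points/year in both columns; SD 6 to 15; splits 50/50, 70/30 and 80/20; normal data, all 100 patients evaluable. Only the ratio d = decline/SD matters, so varying SD at a fixed decline also covers varying the decline. The range is d = 5/6 = 0.83 down to 5/15 = 0.33.

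**Formula.** Power in a column of n patients is P(|T| > t(0.975, n-1)), where T is noncentral t with noncentrality d√n. The columns hold different patients, so

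P(discordant) = p1(1 - p2) + p2(1 - p1).

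**One case in full: SD 12, split 70/30, d = 5/12 = 0.417.**
- n = 70: noncentrality 3.49, critical value 1.995, power 0.930.
- n = 30: noncentrality 2.28, critical value 2.045, power 0.597.
- Only the larger column significant: 0.930 × 0.403 = 0.375.
- Only the smaller column significant: 0.597 × 0.070 = 0.042.
- Discordant: 0.375 + 0.042 = 0.417, or 0.416 before rounding the powers, so 42%.

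**All cases, percentage of studies with discordant verdicts on one outcome:**

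| SD | d | 50/50 | 70/30 | 80/20 |
|---|---|---|---|---|
| 6 | 0.83 | 0 | 1 | 6 |
| 8 | 0.63 | 2 | 9 | 24 |
| 10 | 0.50 | 12 | 25 | 44 |
| 12 | 0.42 | 29 | 42 | 57 |
| 15 | 0.33 | 46 | 54 | 64 |

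At zero true decline the figure is 2 × 0.05 × 0.95 = 9.5% at any split.

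**Checks.**
- Simulating the SAP's own rule (Shapiro-Wilk, then t-test or Wilcoxon; 4,000 runs per scenario) at d = 0.4 gave 45% at 70/30 and 59% at 80/20, as the formula does.
- In the same simulations, a direct between-group test on identically declining groups was significant 4.6% to 5.7% of the time.
- With 60 evaluable patients split 42/18, discordance at d = 0.4 is 56%.

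**Whole cohort.** At SD 12 and n = 100 the single test has 98% power, against 93% and 60% in the two columns at 70/30.

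**Precision of a direct comparison.** 80% power needs a difference of (1.96 + 0.84) × √(1/n1 + 1/n2) SD. That is 0.56 SD at 50/50, 0.61 at 70/30 and 0.70 at 80/20, or 6.7, 7.3 and 8.4 points at SD 12. The contrast would be imprecise and belongs in the report as an estimate with its interval.

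**The case against.** Per-column testing is a reading, not something SAP 11 states. The sentence in SAP 9 opens a section on summarising study data, its neighbour concerns summary tables, and SAP 11 never mentions subgroups. SAP 8.3 names all eligible patients as the main population, SAP 12 claims no departure from the protocol, and the mock-up tables that would settle the layout are not available. This stands as a caution. Even so, the wording of SAP 9 covers all statistical analysis and nothing exempts the tests, so the literal reading is the natural one.

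A reader might infer that the two groups will often get opposite verdicts. The documents do not support that. They supply none of the inputs, and when the decline is large relative to its SD discordance nearly vanishes at 50/50 and stays small at 80/20. Nor are the verdicts opposite in direction; they differ only in being significant or not.

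A reader might also infer that the SAP plans to contrast the drugs. It does not. SAP 8.7 disclaims that aim, and SAP 11.6 permits a claim of change from baseline only. The harm lies in how side-by-side asterisks may be read. Column sizes and 95% CIs would be shown, so an attentive reader could see the differing precision.

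Finally, deleting p-values is not enough. For the t-test, a 95% CI that excludes zero is the same event as p < 0.05, so per-column intervals show the same contrast at the same rate. That objection stands in full, and it is why the fix includes a between-group interval.

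**Conclusion.** The point holds in conditional form. On the literal reading of SAP 9, each drug column gets its own test, asterisk and permitted claim, with no between-group estimate, where Protocol 9.7.1 has no drug split. Identical groups can then receive discordant verdicts. How often is unknown from the documents. Under the assumptions above it runs from essentially never (SD 6, 50/50) to about two studies in three (SD 15, 80/20) per outcome, against about 5% for a direct comparison. That two one-group verdicts are not a comparison does not depend on those assumptions.

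Separately, and without any assumption, SAP 8.7 and SAP 11 contradict each other on whether hypotheses will be tested. Both matters affect reporting, not data collection.

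**What to change.** 1. State in SAP 9, 11.3, 11.4 and 11.6 that the tests and the claim rule apply to the whole eligible cohort of SAP 8.3, as in Protocol 9.7.1.
2. Show the two drug columns descriptively, with N, mean, SD and 95% CI, and without p-values or asterisks.
3. If those columns are presented side by side, add the between-group difference with a 95% CI. Label it descriptive and non-causal, because the groups are defined by ever-use during follow-up.
4. Reconcile SAP 8.7 with SAP 11, so that the plan says once whether hypothesis tests are performed and on which population.

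The cost is SAP wording and table shells; no new data are needed. The downside is fewer p-values to quote and a wide between-group interval. At SD 12 and 70/30 its half-width is about 1.98 × 12 × √(1/70 + 1/30) = 5.2 points/year, as large as the assumed decline itself.

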11.2 ADVERSE EVENT AND SERIOUS ADVERSE EVENT COLLECTION AND REPORTING

The investigator shall maintain and keep detailed records of all AEs in their patient files.

Collection of AEs

The study design is of non-interventional nature and the study is conducted within the conditions of the approved marketing authorization. Sufficient data from controlled interventional trials are available to support the evidence on the safety and efficacy of the studied BI drug. For this reason, the following AE collection and reporting requirements have been defined.

The following must be collected by the investigator in the paper CRF from signing the informed consent onwards until the end of the study:

- All adverse drug reaction (ADRs) (serious and non-serious),
- All AEs with fatal outcome,

All ADRs including those persisting after study completion must be followed up until they are resolved, have been sufficiently characterized, or no further information can be obtained.

The investigator should carefully assess whether an AE constitutes an ADR using the information below.

Causal relationship of adverse event

The definition of an adverse reaction implies at least a reasonable possibility of a causal relationship between a suspected medicinal product and an adverse event. An adverse reaction, in contrast to an adverse event, is characterized by the fact that a causal relationship between a medicinal product and an occurrence is suspected.

Medical judgment should be used to determine the relationship, considering all relevant factors, including the pattern of reaction, temporal relationship, de-challenge or re-challenge, and confounding factors such as concomitant medication, concomitant diseases, and relevant history.

Non-interventional Study Protocol
BI Study Number 1199-0303**c16462309-02**

Proprietary confidential information © 2017 Boehringer Ingelheim International GmbH or one or more of its affiliated companies

Arguments that may suggest a **reasonable causal relationship** could be:

- The event is **consistent with the known pharmacology** of the drug
- The event is known to be caused by or **attributed to the drug class**.
- A **plausible time to onset of the event** relative to the time of drug exposure.
- Evidence that the **event is reproducible** when the drug is re-introduced
- **No medically sound alternative etiologies** that could explain the event (e.g. preexisting or concomitant diseases, or co-medications).

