1. Age, gender, race, education level, environmental/occupation exposures, height, weight, and BMI.
2. HRCT, surgical lung biopsy, multidisciplinary team (MDT) diagnosis, and UIP pattern.
3. Cough, dyspnea, fatigue, weight loss, dizziness, chest pain, anxiety, aching muscles and joints, clubbed fingers, require oxygen therapy (device), or others (according to physicians' judgment and should be specified on the CRF)
4. STOP-Bang Scoring Model data will be collected to assess if patients have obstructive sleep apnea, and Berlin questionnaire results will only be collected from those with suspected/confirmed obstructive sleep apnea according to STOP-Bang Scoring Model.
5. Concomitant medications used for treating comorbidities within 6 months prior to enrolment will be collected.
6. Anti-fibrotic drugs (i.e., nintedanib and pirfenidone) used within 6 months before baseline will be recorded.
7. Spirometry data include FVC, DLCO, SpO₂, TLC, IC, etc.
8. OFEV relevant ADR (serious and non-serious), fatal AEs, and pregnancies.
9. Hct, Hb, platelets, RBC, WBC, neutrophils, lymphocytes, monocytes, eosinophils, basophils, CRP, CK, rheumatoid factor, antinuclear Ab, anti-Jo1 Ab, Sjogrens SS-A or SS-B Ab, scleroderma-70 Ab, c-ANCA, and p-ANCA, etc..
10. PDGF, VEGF, FGF, etc..
11. MUC5B, etc..

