10.4 Safety Endpoints

- Frequency of adverse events and serious adverse events.

All adverse events will be summarized with the coding term, severity, and relationship to nintedanib by frequency tables with the counts and percentage.

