11.5 Safety Analyses

- Frequency of adverse events and serious adverse events.
 - AEs and SAEs will be summarized as number of AEs, number of subjects with AEs and percentage of subjects with AEs. The summary will be further categorized by the seriousness, severity, causality, and outcome.
 - AE will be coded using the MedDRA dictionary. All adverse events will be classified using MedDRA terminology. The number of subjects and percentage of subjects will be computed by System Organ Class and Preferred Term to show the incidence of AE. The incidence of AE will be categorized by the severity. The incidence of AE by the severity will be presented as a separate table. Number of events and number of subject with events will be included in the summary table.
 - The incidence of AEs suspected related to nintedanib will be computed per the MedDRA terms. Number of suspected events and the number of subjects with suspected event with the corresponding percentage will be listed. The incidence of AEs suspected related to nintedanib will also be categorized by the severity.

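### The SAP's with/no anti-fibrotic columns are not comparable for non-fatal adverse events, because those events are recorded only when attributed to a drug (OFEV alone under the visit rule)

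*SAP*

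**What the plan says.** **Layout.** SAP 9 applies the split by anti-fibrotic use to everything: "All the statistical analysis will be performed and categorized by the subgroup of with anti-fibrotic drug and no anti-fibrotic drug". It then fixes the format: "The summary tables will be tabulated with columns of the two subgroups". SAP 8.4 puts a patient in the 'with' group on one or more records of either nintedanib or pirfenidone, and in the 'no' group if no such record exists during observation. Pirfenidone-only patients are therefore in 'with'.

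**Safety tables.** SAP 10.4 says: "All adverse events will be summarized with the coding term, severity, and relationship to nintedanib by frequency tables with the counts and percentage". SAP 11.5 counts AEs, serious AEs and subjects with AEs, and adds: "The summary will be further categorized by the seriousness, severity, causality, and outcome". It also plans separate incidence tables for events suspected to be related to nintedanib. Neither section exempts safety from the two columns or warns about reading across them.

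**Collection.** Footnote 8 of the schedule, in both documents, limits safety reporting to "OFEV relevant ADR (serious and non-serious), fatal AEs, and pregnancies". The visit lists in Protocol 9.2.3 carry the same limit at baseline, Week 4 and Weeks 16 to 100. Protocol 11.2 is wider. Its list of what goes on the CRF begins "All adverse drug reaction (ADRs) (serious and non-serious", names no drug, and adds every AE with a fatal outcome. Two further scopes appear. The expedited-reporting table in 11.2 asks for fatal AEs only in OFEV-exposed patients, and Protocol 9.7.3 assumes that all serious AEs are available.

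**The concern.** A side-by-side AE table invites the reader to compare its columns. That is fair only if an event of a given kind has the same chance of being recorded in each. Here a non-fatal event must pass an attribution step first, and that step is open to some patients and closed to others according to the drug they take, which is also what defines the columns.

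At stake is the descriptive safety output: the percentage of subjects with any AE and the breakdowns by seriousness, severity, causality and outcome. The lung-function endpoints are not affected. Correcting the title or the denominator alone would not be enough, since two unequally ascertained columns would remain.

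**Working it through.** The plan states no AE rate, drug mix or safety calculation, so there is no figure to reproduce. The check sets the texts side by side and then asks what can be said about size.

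**Step 1. What each rule lets in.**

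| Event | Visit lists and footnote 8 | Protocol 11.2 CRF list | SAP column |
|---|---|---|---|
| Fatal AE | recorded | recorded | either |
| Non-fatal reaction to nintedanib | recorded | recorded | 'with' |
| Non-fatal reaction to pirfenidone | not recorded | recorded, but shown as not related to nintedanib | 'with' |
| Non-fatal reaction to another medicine | not recorded | recorded, but shown as not related to nintedanib | either |
| Non-fatal AE not attributed to a medicine | not recorded | not recorded | either |

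Only the first row is collected alike in all patients under both rules.

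- *Narrower rule.* The 'no' column holds essentially fatal AEs alone. The 'with' column mixes nintedanib users, whose non-fatal reactions count, with pirfenidone-only users, whose reactions do not. Death is itself a seriousness criterion (Protocol 11.1), so seriousness and outcome in the 'no' column follow from the collection rule.
- *Wider rule.* Untreated patients can contribute reactions to other medicines. Anti-fibrotic users have that route and one more. The last row stays empty everywhere, and the causality split asks only about nintedanib, which has no meaning in the 'no' column.

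**Step 2. Can the size or direction be derived?** Let dW and dN be the risks of a fatal AE in 'with' and 'no', and x the chance that a 'with' patient has a recorded non-fatal event, taken as independent of death. Under the narrower rule:

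- recorded any-AE in 'with' = 1 − (1 − dW)(1 − x)
- recorded any-AE in 'no' = dN
- difference = (dW − dN) + x(1 − dW), which is positive only if x > (dN − dW)/(1 − dW)

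The quantity x depends on the non-fatal event risk p, the share a of patients with such events who have one attributed to OFEV, and the share q of the 'with' column on nintedanib: x = p × a × q. The documents give none of the three.

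*The mechanism is real.* Assume identical true risks in both columns: d = 0.20 and p = 0.60, so the true any-AE risk is 1 − 0.80 × 0.40 = 68% in each. With a = 0.6 and q = 1, x = 0.36 and the recorded figures are 1 − 0.80 × 0.64 = 48.8% and 20.0%. With a = 0.3 and q = 0.5, x = 0.09 and they are 1 − 0.80 × 0.91 = 27.2% and 20.0%. A true difference of zero becomes 28.8 or 7.2 points, purely according to assumed inputs. These are illustrations, not estimates for this study.

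*The direction is open.* Protocol 7 cites median survivals of 3 years and 0.9 year. Over 100 weeks (700/365.25 = 1.916 years), assuming exponential survival and one fatal AE per death, the risks are 1 − 0.5^(1.916/3) = 0.358 and 1 − 0.5^(1.916/0.9) = 0.771. Purely to test the sign, put the lower risk in 'with' and the higher in 'no'. The 'with' column then looks worse only if x exceeds (0.771 − 0.358)/(1 − 0.358) = 0.64. With equal mortality, any x above zero suffices. The documents do not say which situation applies.

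**The case against.** **No comparison is planned.** The protocol calls the study essentially descriptive, SAP 8.7 disclaims any aim of showing differences between treatment groups, and no between-column AE test is specified. This stands and lowers the severity. It does not help a reader faced with two adjacent percentages and no caveat.

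**The layout is inferred.** The mock-up tables are not among the documents, and SAP 11.5 does not mention columns. This also stands in part: the point rests on the unqualified wording of SAP 9.

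**A zero for untreated patients is natural.** Someone who never took nintedanib cannot react to it, so a table titled as nintedanib reactions and deaths would explain itself. That is a good argument for retitling. The SAP, however, presents the content as all adverse events and adds seriousness, severity and outcome.

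**Stronger readings that a reader might infer, and why they fail.**

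- *The 'no' column is all fatal and serious in every case.* This fails under Protocol 11.2, where untreated patients can contribute non-fatal reactions to other medicines. Even under footnote 8, a patient who took OFEV only before baseline could fall in 'no' with a recorded reaction, and pregnancies are also listed.
- *Setting an assumed nintedanib reaction risk against zero gives the size of the artefact.* It does not. That gap would be the true incidence of drug reactions against a structural zero. An artefact needs unrecorded background events, for which the documents give no rate.
- *Treated patients will look worse.* This depends on mortality being similar in the two groups, as Step 2 of the working shows.
- *The whole difference between columns is an artefact.* The CRF list in Protocol 11.2 takes fatal AEs from all patients, so a difference in deaths is not produced by the collection rule.

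**Conclusion.** The point holds as a should-fix matter of analysis layout. Taken as written, SAP 9 with SAP 10.4 and 11.5 gives AE columns with unequal ascertainment. Neither collection rule makes them comparable for non-fatal events or for any summary that includes them.

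Size and direction cannot be stated. They depend on AE rates, attribution, drug mix and mortality by group, none of which the documents supply. The conclusion assumes that SAP 9 governs the safety tables, which cannot be checked against the table shells. The harm is a misleading descriptive table; no formal inference and no primary endpoint is affected.

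**What to change.** 1. In SAP 9 and 11.5, exempt non-fatal events from the with/no columns. Tabulate non-fatal ADRs by the drug actually taken, with patients exposed to that drug as the denominator.
2. Reconcile footnote 8 and the visit lists with Protocol 11.2 on whether ADRs to drugs other than OFEV are recorded. If they are, tabulate causality against the suspected drug. If they are not, leave pirfenidone-only patients out of the ADR table.
3. Report fatal AEs overall. If they are also shown by column, state that SAP 8.4 assigns 'with' on any drug record during follow-up, so patients who die early have less chance to enter that group.
4. Title the tables as ADRs and fatal AEs, and state that non-fatal events are not compared between treated and untreated patients.

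**Cost.** SAP wording and revised table shells before database lock, plus a clarification of which collection rule applies. The drug records needed are already on the CRF (Protocol 9.3.1), and no new patients or procedures are required. The downside is the loss of a treated-versus-untreated AE column, which the data cannot support.

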8. RESEARCH QUESTION AND OBJECTIVES

The primary objective is to characterize the IPF population in Taiwan with regard to their clinical course under clinical practice conditions in Taiwan.

The secondary objectives are to understand the clinical characteristics and quality of life of IPF population in Taiwan.

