The limitations created by a small sample size can have profound effects on the outcome and worth of a study. A small sample size may increase the data variability and have extremely detrimental effects. Therefore, when looking into the study outcome, study statisticians will determine whether the small sample size limitations will have a negative impact on study's results before getting underway; and if it does, study statisticians will not perform stratified analyses. Also, study results will be elaborated carefully because a small sample size may deviate the true results of the real-world population.

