12 SUMMARY OF CHANGES TO THE PROTOCOL

The initial statistical analysis plan will follow the protocol design and no changes or differences will be planned in the initial statistical analysis plan.

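### SAP 9 specifies results only by anti-fibrotic subgroup; no SAP text states that outcomes are also reported for all eligible patients, whom the primary objective concerns

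*SAP*

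**What the plan says.** SAP 9 sets a general rule: "All the statistical analysis will be performed and categorized by the subgroup of with anti-fibrotic drug and no anti-fibrotic drug". The layout follows from it: "The summary tables will be tabulated with columns of the two subgroups". Population sizes are to be annotated in the tables, but no total or overall column is mentioned there or anywhere else in the SAP.

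SAP 8.4 defines the two groups by whether the patient had any anti-fibrotic record during observation. It plans the split without a condition: "Subgroup analysis will be conducted based on the prescription of nintedanib and pirfenidone".

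The protocol is oriented differently. Its primary objective (section 8, repeated in SAP 6.1.1) is to "characterize the IPF population in Taiwan with regard to their clinical course". Protocol 9.7 and SAP 8.3 both define the main analysis population as all eligible patients. Protocol 9.7.1 describes a single mean annual change covering at most two years, and Kaplan-Meier estimates for exacerbation and death, with no division by drug.

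Protocol 9.9 attaches a prior judgement to any stratification. The statisticians are first to assess whether the limited number of patients harms the findings, and the consequence is stated: "if it does, study statisticians will not perform stratified analyses".

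**The concern.** The only presentation that the SAP spells out is by anti-fibrotic subgroup, whereas the study's main question is about the whole cohort. A programmer who follows SAP 9 to the letter would produce two sets of estimates and no result for the population that the objective names.

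At stake is the headline result of a descriptive study: the annual decline in lung function, the annual change in SGRQ, CAT and 6MWT, and the time to first exacerbation and to death, each for Taiwanese IPF patients as a whole. The split also spreads about 100 patients over two columns of unknown size, and the SAP does not record the sample-size judgement that protocol 9.9 places ahead of stratified analyses.

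**Working it through.** **Step 1. Set the texts side by side.**

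| Item | Whole cohort | By anti-fibrotic use |
|---|---|---|
| Primary objective (protocol 8, SAP 6.1.1) | Yes | Not mentioned |
| Main analysis population (protocol 9.7, SAP 8.3) | Yes | Not mentioned |
| Main estimate (protocol 9.7.1) | Single mean annual change | Not mentioned |
| Hypothesis and tests (SAP 11.1 to 11.4) | Consistent with it, not stated | Not mentioned |
| Scope of analysis and table columns (SAP 9) | Not mentioned | Yes, for all statistical analysis |

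Two summaries do not fit the rule in SAP 9. Disposition (SAP 9.1) uses screened subjects as a denominator, and screen failures cannot sensibly be classed by later drug use. Exposure (SAP 10.1) is summarised by drug. Neither is a whole-cohort result for an outcome.

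**Step 2. What could be recovered from two columns?** SAP 9 asks for n, mean, median, SD, range and 95% CI in each. With n1, m1, s1 and n2, m2, s2 from the two columns and N = n1 + n2:

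- Overall mean = (n1·m1 + n2·m2) / N.
- Overall sum of squares = (n1 − 1)·s1² + (n2 − 1)·s2² + (n1·n2/N)·(m1 − m2)². Dividing by N − 1 gives the overall variance.

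So the overall mean, SD, t-based CI and t-test can be rebuilt, up to the rounding in SAP 8.12. These cannot:

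- the overall median, because two medians do not determine the pooled one;
- the overall Shapiro-Wilk and Wilcoxon results, because both need individual values (SAP 11.2 uses the first to decide whether the second replaces the t-test);
- the overall Kaplan-Meier curve and its quartiles, because they need the pooled event and censoring times.

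**Step 3. Precision.** The plan gives no SD, effect size or precision target behind its approximately 100 patients, so there is no figure of its own to reproduce. As an illustration, the 95% CI half-width of a one-sample mean, in SD units, is t(0.975, n − 1) / √n:

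- n = 100: 1.984 / 10 = 0.198
- n = 50: 2.010 / 7.071 = 0.284
- n = 30: 2.045 / 5.477 = 0.373
- n = 20: 2.093 / 4.472 = 0.468
- n = 10: 2.262 / 3.162 = 0.715

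The documents give no expected share of anti-fibrotic users, so a range of splits of 100 patients is shown:

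| Assumed split | Larger column (SD) | Smaller column (SD) |
|---|---|---|
| 50/50 | 0.28 | 0.28 |
| 70/30 | 0.24 | 0.37 |
| 80/20 | 0.22 | 0.47 |
| 90/10 | 0.21 | 0.72 |

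The whole cohort gives 0.20 SD. All figures assume complete data; missing values would widen every one of them.

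**The case against.** The best defence is that the SAP plainly presupposes an overall analysis. SAP 8.3 names all eligible patients as the main population, and SAP 8.4 presents the split as a subgroup analysis, which implies a main one. SAP 11.1 states a single hypothesis, and SAP 11.4 speaks of the Kaplan-Meier graph in the singular. Column layout belongs in the mock-up tables (SAP 13.1), which were not available and may well have a total column. All of this stands as evidence of intent. A reader might infer that the plan leaves out its main estimate altogether; the documents do not support that. What remains is that the one section which fixes the scope and the columns says something else, and no other text overrides it.

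A reader might also infer that the protocol forbids the split, or that SAP 12 is wrong when it says "no changes or differences will be planned in the initial statistical analysis plan". Neither is established. Protocol 9.9 leaves the matter to the statisticians' judgement, gives no numerical threshold and does not say where the judgement is to be recorded. Protocol 9.7 leaves analytic detail to the SAP, allows further exploratory analyses, and requires an amendment only when a principal feature of the objective changes. For the same reason, no particular minimum subgroup size can be read out of protocol 9.9. In a descriptive study a small column shown with its n and CI is legitimate.

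Finally, a reader might apply the 0.9-year median survival in protocol 7 and conclude that a subgroup could shrink to a handful of patients by Week 100. Under exponential survival the rate is ln 2 / 0.9 = 0.770 per year, and exp(−0.770 × 1.916) = 0.229, or about 23 of 100 alive. That calculation does not describe the primary estimate. The median runs from diagnosis rather than enrolment, the exponential form is an assumption, and the share in the smaller group is unknown. The annualised change (protocol 9.7.1, SAP 10.2) is not confined to patients who reach Week 100.

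**Conclusion.** The point holds as a defect in the text of SAP 9: by-subgroup reporting is the only presentation stated for the outcomes, while the objective, the main analysis population and protocol 9.7.1 call for a whole-population result. Read literally, it loses the overall median, Wilcoxon result and Kaplan-Meier curve. The overall mean and t-test would have to be rebuilt by hand. The estimates that are stated would have half-widths of 0.21 to 0.28 SD in the larger column and 0.28 to 0.72 SD in the smaller one, against 0.20 SD for the cohort. Those figures rest on assumed splits from 50/50 to 90/10 and on complete data; the finding itself does not depend on them.

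No data are lost, and the overall results can still be programmed. The correction should nevertheless be made before database lock, so that the main result is specified in advance. If the mock-up tables already carry a total column, the SAP text only needs to be brought into line with them.

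**What to change.** In SAP 9, state that all eligible patients (SAP 8.3) form the first column and the main result for every primary and secondary outcome, including each test and each Kaplan-Meier curve. Keep the two anti-fibrotic columns as supplementary and descriptive. Make them subject to the statisticians' sample-size judgement in protocol 9.9, and record that judgement in the SAP. Check that the mock-up tables match.

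The cost is one more table column, one more curve for each time-to-event outcome, and a few sentences in the SAP. No new data are needed, and the anti-fibrotic columns can stay if the recorded judgement supports them.
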